#### Urine PK sampling

Nominal Time Point	Window
Predose	Within 60 min before dosing
Voluntary Urine	–
Forced micturition at 24 h after dosing	Nominal time point $\pm$ 30 min

## 7.3. Data Handling Convention for Missing Data

### (1) Non-PK related

#### Adverse events:

If severity or relationship is found to be missing the most severe occurrence will be imputed for the summary of interest.

For AE start missing or partial dates, the AE will be treated as TEAE if it cannot be determined to be a non-TEAE.

#### Other safety:

For safety summaries, only observed data will be used. Unless otherwise specified, missing safety data will not be imputed.

### (2) PK related

For PK summaries, only observed data will be used. Missing PK data will not be imputed. When calculating Ae and Ae%, missing PK data will be imputed to 0.

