9.2.4 Pharmacokinetic assessments

Blood sampling will be performed for measurement of plasma concentrations of unchanged edaravone, sulfate conjugate, and glucuronide conjugate, and urine sampling will be performed for measurement of urine concentrations of them. The investigator (or subinvestigator) or study collaborator will record the dates and times of the blood and urine sampling and the sampled urine volume in the CRF. The measurement will be conducted in the drug concentration measurement site.

If any other assessments are scheduled at the same time point of blood sampling for plasma drug concentration measurement, blood sampling will be performed at the exact scheduled time point, and other assessments will be performed before or after the blood sampling. In principle, a 12-lead ECG and vital signs (except for body temperature) will be measured before the blood sampling for plasma drug concentration measurement and safety assessment. Urine will be forced to void 24 hours after administration. Urine will not be collected from subjects if collection is difficult.

The acceptable time range for the time of each blood or urine sampling (forced void) will be

Confidential

specified in a separate document.

9.2.4.1 Measurement of plasma concentrations of unchanged edaravone, sulfate conjugate, and glucuronide conjugate

Time points and volume of blood sampling

(a) Time points of blood sampling

Day 1	Before investigational product administration, 0.083, 0.25, 0.5, 0.75, 1, 1.5, 2, 4, 6, 8, 10, and 12 hours after administration
Day 2	24 hours after investigational product administration

(b) Frequency of blood sampling: 14

(c) Volume of blood sampling: 5.5 mL, Total: 77 mL (per subject)

9.2.4.2 Measurement of urine concentrations of unchanged edaravone, sulfate conjugate, and glucuronide conjugate

Urine volume will be measured at voiding and the urine specimen will be processed (see Section 9.2.4.3). Urine will be forced to void before administration and 24 hours after administration. Urine will not be collected from subjects if collection is difficult.

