### 3.3. Schedule of Study Procedures

Day (time window)	Informed consent	Screening Day -30 to -2	1																24 h Discharge	2	End-of-study  Assesment Day 8 (±2)
			-1	Admission	Pre-dose	0	5 m	15 m	30 m	45 m	1 h	1 h 30 m	2 h	4 h	6 h	8 h	10 h	12 h			
Time after dosing		Visit																	Visit		
Written informed consent	X																				
Subject characteristics		X																			
Eligibility assessment		X	X	X																	
Dosing of edaravone					X																
Height, weight, BMI a)		X	X																X		
Physical examination		X	X	X														X	X		
Vital signs		X	X	X														X	X		
12-lead ECG		X	X	X														X	X		
Laboratory tests		X	X																X		
Serological tests		X																			
Drug/alcohol abuse screening		X																			
Pregnancy test (only female)		X	X																X		
Adverse events	←																				
Concomitant medications		←																			
Blood sampling for edaravone				X	X	X	X	X	X	X	X	X	X	X	X	X	X	X			
Urine sampling for edaravone b)				←															→		

- a) Height: Only at screening; Body weight: At screening, hospitalization and end-of-study assessment (discontinuation assessment). BMI: At screening and hospitalization assessment.
- b) Urine volume will be measured for each void. A portion of the urine will be collected, dispensed into a tube containing stabilizer, and stored frozen. Urine will be forced to void at 24 hours after administration. Urine will not be collected from subjects if collection is difficult.
- c) At the time of withdrawal, the same tests will be performed as those of the end-of-study assessment.

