## 6.2. Data Review Meeting

Prior to database lock, a data review meeting (DRM) was conducted at November 22, 2019. Protocol deviation and handling of subjects and records, for analysis sets and evaluations, was confirmed during DRM.

No protocol deviation was observed during the study. As a results of DRM, all subject was included in SAF and PK analysis set.

The PK data handling was assessed during DRM. All PK data were considered valid and included in the calculation of PK parameters and in the summary tables and figures.

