### 7.1.3.2. Pharmacokinetic Parameters

Below the limit of quantification

For the calculation of PK parameters, actual sampling time (in hours rounded to 3 DPs) relative to dosing should be used. Concentration below the limit of quantification (BLQ) will be

imputed with a value of 0. For calculation of AUCs, missing data will be treated as if the respective sample never had been scheduled for the calculation by the linear-linear trapezoidal rule. For Ae, Ae% and CLr, geometric mean and geometric CV% will be calculated only when all the individual Ae, Ae% and CLr is greater than 0 in each sampling time point.

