MRT	h	$AUMC_{0-\infty} = \sum_{i=1}^n \frac{(t_i - t_{i-1})(t_i \times C_i + t_{i-1} \times C_{i-1})}{2} + \frac{t \times C_t}{K_{el}} + \frac{C_t}{(K_{el})^2}$ $MRT_{0-\infty} = \frac{AUMC_{0-\infty}}{AUC_{0-\infty}}$
V z /F	L	$V_z/F = CL/F \times \frac{1}{K_{el}}$
V ss /F	L	$V_{ss}/F = MRT \times CL/F$
Number of Kel points	-	will be determined using number of points used in computing Kel. If Kel cannot be estimated, zero.
Lower Limit of Kel	h	will be determined using lower limit on time to be included in the calculation of Kel
Upper Limit of Kel	h	will be determined using upper limit on time to be included in the calculation of Kel
Ae	mg	urine concentration × urine volume
Ae%	%	Ae / Dose
CLr	L/h	$CLr = \frac{Ae}{AUC_{0-\infty}}$

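### SAP 7.3(2) scores missing urine as zero without separating 'no void' from 'urine not collected or lost', so it can bias Ae, Ae% and CLr only downward

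*SAP*

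**What the plan says.** SAP 7.3(2) opens with a general rule, "Missing PK data will not be imputed", and then makes an exception without conditions: "When calculating Ae and Ae%, missing PK data will be imputed to 0". Neither document defines what counts as missing for urine.

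The surrounding text is as follows.

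- **Collection.** SAP 3.3, footnote b: "Urine volume will be measured for each void". SAP 7.2(2) gives voluntary voids no time window; only the pre-dose void and the forced void at 24 h have one.
- **Permitted gaps.** Protocol 9.2.4: "Urine will not be collected from subjects if collection is difficult".
- **Calculation.** SAP Appendix 1 defines Ae as "urine concentration × urine volume", Ae% as Ae over dose, and CLr as Ae over AUC0-∞. The SAP's list of PK parameters describes Ae as cumulative over 0-24 h.
- **Values below quantification.** SAP 7.1.3.2 already sets these to 0.
- **Missing plasma samples.** For AUC, SAP 7.1.3.2 says "missing data will be treated as if the respective sample never had been scheduled".
- **Geometric summaries.** SAP 7.1.3.2 restricts these: "geometric CV% will be calculated only when all the individual Ae, Ae% and CLr is greater than 0 in each sampling time point". The same condition covers the geometric mean.
- **Data review.** SAP 6.2: "No protocol deviation was observed during the study". It adds that all PK data were judged valid and were included.

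**The concern.** Zero is the right contribution from an interval with no void. It is not right for a void that was passed but not collected, whose volume was not recorded, or whose specimen was lost: that amount is unknown and is usually above zero. The wording treats both cases alike. It is not needed for measured values below quantification, which have their own rule, and it runs opposite to the plasma convention, where a missing sample is skipped and not scored zero.

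Ae and Ae% are listed endpoints for all three analytes, and CLr is listed for unchanged edaravone (SAP 2.3). An understated urinary recovery would be reported as an observed result. Because the protocol allows urine to go uncollected, such a gap can arise without being logged as a deviation.

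**Working it through.** The plan gives no figure to reproduce. The sample size of 9 is stated not to rest on a statistical calculation (Protocol 6.1, SAP 3.4). The check has two parts: the direction of the error, and its size under stated assumptions.

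**Direction.** For one subject and analyte, Ae = Σ(Cᵢ × Vᵢ) over the voids in 0-24 h, with every term at least 0. Replacing an unknown term by 0 gives Ae(imputed) ≤ Ae(true), with equality only if that void truly held no drug. If a fraction f of the true amount is lost:

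- Ae becomes (1 − f) × Ae(true).
- Ae% = Ae/Dose falls by the same fraction, because the dose is fixed.
- CLr = Ae/AUC0-∞ falls by the same fraction, because AUC0-∞ comes from plasma and does not depend on urine.

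No route leads upward.

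**Size, case (a): one subject with no urine, scored 0.** Inputs: N = 9 (SAP 3.4). Assumption: this subject's true value equals the mean of the other eight, scaled to 1.

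- Mean with the zero = 8/9 = 0.889, a change of −1/9 = −11.1%. The minimum becomes 0.
- If the other eight have SD c (assumed), the SD of all nine = √[(7c² + 8(1/9)² + (8/9)²)/8], and CV% = 100 × SD/(8/9).

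| CV% of the other eight (assumed) | SD of all nine | CV% of all nine |
|---|---|---|
| 20 | 0.382 | 43.0 |
| 30 | 0.436 | 49.0 |
| 50 | 0.574 | 64.6 |

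- One value is now not above 0, so SAP 7.1.3.2 withholds the geometric mean and geometric CV% for the affected parameter.

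**Size, case (b): one missed void in one subject.** Assumptions: the void holds a share s of that subject's excretion, and the nine subjects are alike in true Ae. The arithmetic mean changes by −s/9, and the geometric mean by (1 − s)^(1/9) − 1.

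| Share s (assumed) | That subject's Ae | Group arithmetic mean | Group geometric mean |
|---|---|---|---|
| 10% | −10% | −1.1% | −1.2% |
| 25% | −25% | −2.8% | −3.1% |
| 50% | −50% | −5.6% | −7.4% |

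In case (b) every value stays positive, so the geometric summaries are still printed and nothing in them shows that a collection was incomplete.

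**Does another rule close the gap?** None does. The itemised PK cases in Protocol 13.3(1) concern blood specimens and plasma concentrations. The urine table in SAP 7.2(2) has no completeness criterion.

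**The case against.** Five arguments can be made for leaving the rule as a minor matter.

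1. **The intended reading may be narrower.** SAP 7.3(2) also restricts PK summaries to observed data. On that reading zero is added only for an empty interval, and a subject with no urine is left out, so case (a) would not occur. This is possible, but the SAP does not say so. The condition that geometric statistics need all values above zero shows that zeros are anticipated. The narrow reading also leaves the uncollected or lost void scored as zero.

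2. **The permission not to collect looks like an exemption for a whole subject, not for single voids.** If so, permitted gaps are of the case (a) kind, which depends on point 1. It does not remove the ambiguity.

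3. **An unrecorded voluntary void leaves no record to impute.** Ae would then be too low even with the sentence deleted. This stands: the sentence causes the error mainly where a void is known but its volume or concentration is missing, or where a whole collection is absent. It is also why a statement on completeness is needed alongside the rewording.

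4. **The data review meeting found nothing wrong.** SAP 6.2 reports no deviations and valid PK data. But permitted non-collection is not a deviation, and valid describes the data that exist; SAP 6.2 does not say that urine was complete.

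5. **The stakes are low.** The study is descriptive. Patients must need no help with eliminating (Protocol 3.2), Protocol section 1 says ALS is not accompanied by dysuria, and the collection takes place in hospital. Difficult collection should therefore be uncommon. This stands and limits how often the rule would act, but not whether it gives the right value when it does.

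**Conclusion.** The concern holds. As written, the rule assigns zero to an unknown amount whenever urine was passed but not collected, measured or kept, and the resulting error in Ae, Ae% and the CLr of unchanged edaravone has one direction. This is an incorrect rule and not merely a missing detail.

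The effect is conditional. Whether any urine was missing in this trial cannot be told from the documents, so no actual bias is shown. The sizes derived above rest on assumed shares, assumed CVs and subjects alike in true excretion. The whole-subject case depends on reading the rule as applying to a subject with no urine at all, which the text does not exclude. The change should be made, because with 9 subjects a single instance is visible in the group summary and the correction is simple.

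**What to change.** Replace the sentence in SAP 7.3(2) with a rule to this effect: zero is used only where it is confirmed that no void occurred (measured values below quantification are already 0). Where a void was not collected, or its volume or concentration is missing, cumulative Ae and Ae%, and CLr for unchanged edaravone, are reported as NC for that subject and analyte and left out of the summaries, with n shown. Partial amounts are listed with a flag. In addition, state in the SAP or the study report whether each subject's 0-24 h urine collection was complete.

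The cost is one sentence and one status per void or interval (no void, collected, not collected or lost). There are two drawbacks. First, n for urinary parameters may fall below 9, and one small lost void removes an otherwise observed profile from the summary; the flagged listing keeps those partial data visible. Second, the SAP text postdates the data review meeting, so the status may have to be rebuilt from source records and may not be recoverable for every void. If all collections were complete, no result changes.

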## 8. STATISTICAL METHODOLOGY

### 8.1. Study Subjects

#### 8.1.1. Subject Disposition

Subject disposition will be summarized on the SAF and listed on the enrolled subjects.

#### 8.1.2. Analysis Populations

Analysis populations including the inclusion and exclusion criteria deviation at screening will be summarized and listed on the enrolled subjects.

#### 8.1.3. Study Drug Exposure

Exposure data will be listed on the SAF.

#### 8.1.4. Demographic and Other Baseline Characteristics

The following demographic and other baseline characteristics will be used.

	Category	descriptive
Sex	Male, Female	
Age at informed consent(years)		Yes
Height(cm)		Yes
Weight(kg)		Yes
BMI(kg/m  )		Yes
Race	Japanese	
El Escorial Revised Airlie House Criteria	Clinically definite ALS, Clinically probable ALS, Clinically probable-laboratory-supported ALS	
Total ALSFRS-R Score		Yes
Medical History	No, Yes	
Complication	No, Yes	
Concomitant Medication	No, Yes	
Allergic History (including drug allergies)	No, Yes	
Drinking status	No (if 'Never'), Yes (if otherwise)	
Smoking Status	No (if 'Never'), Yes (if otherwise)	
Edaravone History	No, Yes (if any record at "Edaravone Intravenous History")	

Demographic and other baseline characteristics will be summarized and listed on the SAF.

### **8.1.5. Medical History and Allergic History**

Medical history and allergic history will be listed on the SAF.

### **8.1.6. Prior or Concomitant Medications**

Prior medication and concomitant medication will be listed on the SAF.

## **8.2. Efficacy Assessments**

N/A

## **8.3. Safety Assessments**

Safety assessments will be made on the SAF.

### **8.3.1. Adverse Events**

Overall summary for the following will be conducted.

- Subjects with at least one TEAE
- Subjects with at least one adverse drug reaction
- Subjects with at least one TESAE
- Subjects with at least one serious adverse drug reaction
- Subjects with TEAE leading to death

The following summaries also will be conducted. These table will be ordered by International Agreed Order for SOC and then by alphabet order for PT.

- TEAEs by SOC and PT
- Adverse drug reactions by SOC and PT
- TEAEs by SOC, PT and severity

Each of the summaries will be done at the subject level - multiple occurrences of the same event within a subject will be counted once in the summaries by SOC and PT; multiple occurrences of the same event within a subject will be counted once in the maximum severity category (severe > moderate > mild) and/or maximum drug relationship category (reasonable possibility/no reasonable possibility) and/or the earliest duration.

All AEs, TEAEs and SAEs will be listed.

### **8.3.2. Laboratory Tests**

Absolute values and changes from baseline, except for urinalysis will be summarized by scheduled visit.

For urinalysis, number and percentage will be presented. Shift tables will present the changes in clinically relevant categories from baseline to each scheduled post-baseline visit.

Below in a list of the laboratory test.

Laboratory Test	Parameters
Hematology	Hemoglobin, hematocrit, red blood cell count, white blood cell count, platelet count, MCH, MCHC, MCV, differential white blood count
Biochemistry	Na, K, Cl, Ca, inorganic phosphorus, urea nitrogen, creatinine, uric acid, total bilirubin, direct bilirubin, ALT, AST, $\gamma$ -GTP, ALP, LDH, CK, amylase, total cholesterol, triglycerides, LDL-C, HDL-C, total protein, albumin, glucose
Coagulation	Prothrombin time, activated partial thromboplastin time
Urinalysis	pH, specific gravity, protein, glucose, occult blood, urobilinogen, bilirubin, ketones, sediment (listing only), hCG (listing only)

All data including clinically relevant flagged will be listed. Any BLQ data will be treated as 0 in summary statistics.

### 8.3.3. Vital Signs

Absolute values and changes from baseline will be summarized for the following parameters by scheduled visit.

- Systolic Blood Pressure (mmHg)
- Diastolic Blood Pressure (mmHg)
- Pulse Rate (beats/min).
- Body Temperature(°C)

Vital signs data will be listed.

### 8.3.4. 12-Lead ECGs

Absolute values and changes from baseline will be summarized for the following parameters by scheduled visit.

- Heart Rate (beats/min)
- PR (msec)
- RR (msec)
- QRS (msec)
- QT (msec)
- QTcF (msec)

The percentage of subjects with 12-lead ECG values outside pre-defined limit will be summarized by scheduled visit.

12-Lead ECG data (including overall evaluation) will be listed.

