If blood sampling and a 12-lead ECG or vital sign (except for body temperature) measurement are scheduled at the same time point, blood will be drawn after the 12-lead ECG or vital sign (except for body temperature) measurement.

Time points

Screening	No specifications
Hospitalization (Day -1)	No specifications
Day 1	Before investigational product administration
Day 2	24 hours after investigational product administration
End-of-study assessment or withdrawal assessment	No specifications

(3) 12-lead ECG

After at least a 5-minute rest in a lying position, a 12-lead ECG will be recorded at the time points shown in the table below. Measurement will be done in the fasting state. The investigator (or subinvestigator) will record the date and time of measurement, heart rate, QTcF, PR interval, QT interval, RR interval, QRS interval, and findings in the CRF.

Confidential

If blood sampling and a 12-lead ECG or vital sign (except for body temperature) measurement are scheduled at the same time point, blood will be drawn after the 12-lead ECG or vital sign (except for body temperature) measurement.

Time points

Screening	No specifications
Hospitalization (Day -1)	No specifications
Day 1	Before investigational product administration
Day 2	24 hours after investigational product administration
End-of-study assessment or withdrawal assessment	No specifications

(4) Physical examination

At the times shown in the table below, the investigator (or subinvestigator) will examine the subject and record the examination date and findings in the CRF.

Time points

Screening	No specifications
Hospitalization (Day -1)	No specifications
Day 1	Before investigational product administration
Day 2	24 hours after investigational product administration
End-of-study assessment or withdrawal assessment	No specifications

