### 7.1.2.3. 12-Lead ECG

#### (1) Criteria for pre-defined limit

12-lead ECG:

- QTcF > 500msec
- 500 >= QTcF > 480msec
- 480 >= QTcF > 450msec
- QTcF <= 450 msec
- Change from baseline in QTcF > 30 msec
- Change from baseline in QTcF > 60 msec

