## 7.2. Analysis Visit Definitions

### (1) Non-PK related

The date of the first dose of study drug is defined as Day 1.

Unless otherwise specified, baseline will be the last observed value of the parameter of interest prior to the first intake of study drug (this includes unscheduled visits). No analysis visit window will not be performed for safety evaluation.

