9.3. Analysis Visits to Report

(1) Non-PK related

Safety:

Analysis Visit	Apply to		
	Laboratory Tests	Vital Signs	12-Lead ECGs
Screening	X	X	X
Day -1	X	X	X
Day 1		X	X
Day 2		X	X
Follow up	X	X	X

Screening, unscheduled visits and retests (same visit number assigned) will not be displayed in

by-visit summary tables, but will be included in the data listings.

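### QTcF limits are summarised only at scheduled visits, so an exceedance seen only on an unscheduled or repeat post-dose ECG would enter no ECG-limit table

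*SAP*

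**What the plan says.** SAP 7.1.2.3 sets six QTcF criteria. Four are bands of the absolute value, running from "QTcF <= 450 msec" up to "QTcF > 500msec". The other two are increases from baseline of more than 30 msec and more than 60 msec.

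SAP 8.3.4 gives the only tabulation of these criteria: "The percentage of subjects with 12-lead ECG values outside pre-defined limit will be summarized by scheduled visit".

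SAP 9.3 then says which records such tables may contain: "Screening, unscheduled visits and retests (same visit number assigned) will not be displayed in" and, continuing over the page, "by-visit summary tables, but will be included in the data listings".

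Neither section defines a worst-value or any-time summary. For baseline the rule differs: SAP 7.2 takes the last value before dosing and expressly allows it to come from an unscheduled visit.

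**The concern.** A limit table is read to answer one question: did any subject cross the line after dosing? A table built visit by visit from scheduled records alone cannot answer it when the crossing was measured on some other record. The four absolute bands cover every possible value, so a subject with a normal scheduled Day 2 ECG and an abnormal repeat sits in the lowest band for Day 2, and nothing else in the table shows the repeat.

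At stake is the completeness of the QTcF summary. A reader who relies on the table could see no subject above a limit although one was measured above it.

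**Working it through.** **Inputs.**

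- Number of subjects: 9, stated as not statistically derived (Protocol 6.1, SAP 3.4).
- Limits: the six criteria of SAP 7.1.2.3.
- Scheduled ECGs (Protocol 9.2.5.1, item 3): screening, Day -1, pre-dose on Day 1, Day 2 at "24 hours after investigational product administration", and the end-of-study or withdrawal visit. Only the last two are post-dose.
- Records excluded from by-visit tables: screening, unscheduled visits and retests (SAP 9.3).

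The plan states no figure on this point, so there is none to reproduce.

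**Applying the rule.** The QTcF values here are assumed for illustration. Nine subjects have 420 msec at every scheduled ECG, except where stated.

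| Case | By-visit table, over 500 msec | Any time after dosing, over 500 msec |
|---|---|---|
| A. One subject: scheduled Day 2 value 420, retest 505 | 0/9 (9/9 in the lowest band) | 1/9 (8/9 in the lowest band) |
| B. One subject: scheduled Day 2 value 505, retest 420 | 1/9 | 1/9 |
| C. No extra records; one exceedance on Day 2 and one at follow-up | 1/9 and 1/9 | 1/9 if the same subject, 2/9 if two subjects |

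In case A the increase from baseline is 505 − 420 = 85 msec, so both change criteria are also met on the retest and also missing from the table. Case B shows that the gap does not arise when the scheduled value is the abnormal one. Case C shows that by-visit counts do not give the per-subject count even without extra records.

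**Size.** 1/9 = 0.111, or 11.1 percentage points per subject. The exact (Clopper-Pearson) 95% interval is 0 to 33.6% for 0/9 and 0.3 to 48.2% for 1/9. These overlap widely: the difference is in what is reported, not in what can be inferred about a rate.

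**Other routes to a summary table.** Protocol 9.2.5.2 treats an abnormal finding as an adverse event if it is linked to a sign or symptom, is treated, changes dosing, or is otherwise judged clinically significant. SAP 8.3.1 summarises treatment-emergent events per subject without regard to scheduled visits. The numeric limits of SAP 7.1.2.3 are not among those criteria. An asymptomatic, untreated exceedance that the investigator does not judge significant would therefore be in the listing only.

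**Where such a record could arise.** Protocol section 1 reports peak plasma concentration 0.4 to 0.8 hours after a fasting dose of the suspension. The first scheduled post-dose ECG is at 24 hours. Any ECG recorded near the peak would be unscheduled and so outside the table. This shows a possible source, not that such a recording was made.

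**The case against.** The strongest reply is that nothing in the planned table is wrong. It is labelled by scheduled visit, and an unscheduled recording does not belong to a scheduled visit. That stands. A reader might infer that the plan miscounts an exceedance as a non-exceedance, or biases the percentages downwards. The documents do not support this, because there is no overall count to be wrong. That the count can only be too low is true only against a worst-value measure, which the plan never promised.

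Secondly, no record is lost. All ECG data are listed (SAP 8.3.4), unscheduled and repeat records included (SAP 9.3), and a listing of 9 subjects can be read in full. Findings judged clinically significant also reach the adverse event tables. This stands and limits the consequence, but it leaves the asymptomatic exceedance described above.

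Thirdly, a repeat prompted by an abnormal scheduled value does no harm, since that value stays in the table (case B). The allowance for unscheduled baselines has an ordinary explanation too: the retest described in Protocol 8.2 is done before dosing. A reader might take the asymmetry as designed to flatter the results; nothing in the text suggests so. Nor do the documents mention symptom-triggered ECGs, only unscheduled visits and retests.

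Finally, a reader might extend the point to laboratory data, because SAP 8.3.2 says "Shift tables will present the changes in clinically relevant categories from baseline to each scheduled post-baseline visit". That extension is not supported as it stands. The sentence follows directly on the urinalysis sentence, and Protocol 13.4.3 confines the shift table to urinalysis. The laboratory flags in SAP 7.1.2.2 run in both directions (low, high or abnormal), so a worst value is undefined for parameters that can be abnormal either way.

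**Conclusion.** The point holds for QTcF as a gap in the summaries, not as an error in them. A post-dose exceedance found only on an unscheduled ECG, or on a retest worse than the scheduled value, enters no ECG-limit table, and no per-subject count over the whole post-dose period is planned. One such subject is 11.1 percentage points: 0/9 tabulated against 1/9 measured.

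This assumes that such a record exists, which the documents do not show, and reads SAP 9.3 as applying to the limit table, which SAP 8.3.4 makes a by-visit table. The study's objective is pharmacokinetic and the listings are complete, so this is an inexpensive improvement and no threat to the study's conclusions.

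**What to change.** Keep the by-visit rows. Add one row to the QTcF limit table for any time after dosing, and one sentence to SAP 8.3.4, for example: *For each subject, the highest post-dose QTcF and the largest post-dose increase from baseline, taken across scheduled, unscheduled and retest ECGs, will be classified by the limits in Section 7.1.2.3 and summarised as any time after dosing.* Add to SAP 9.3 that its exclusion does not apply to this row.

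The cost is one row and these two short statements; no new data and no design change are needed. If the row is added after data lock, Protocol 13.5 requires the change and its reason to be given in a revised SAP and the Clinical Study Report, with results before and after the addition kept apart. Leave the laboratory shift tables as they are unless their scope and the direction of a worst value are first defined.
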